1.0 Objectives

1.1 Describe the purpose, specific aims, or objectives of this research.

Response: The purpose of this proposed work is to assess the feasibility of recruiting and administering a short session high intensity interval training regimen to older adults (60-90 years of age), as well as performing routine physical performance and quality of life assessments, and obtain blood samples for analysis of inflammatory biomarkers, testosterone, and serum microRNA.

After 20-months of COVID-19 restrictions, we will contact previously enrolled participants and ask them to return for 1 follow-up visit in order to investigate changes in physical fitness, muscle strength, physical activity, functional capacity, and microRNA profiles among participants who completed our short-session high intensity interval training program, 16-months previously. This will be conducted to explore possible de-training-associated loss of fitness, function, and quality of life among participants who previously completed a 12-week HIIT intervention.

1.2 State the hypotheses to be tested, if applicable.

NOTE: A hypothesis is a specific, testable prediction about what you expect to happen in your study that corresponds with your above listed objectives.

Response: We hypothesize that we will demonstrate adequate recruitment rates and low attrition rates such that we can justify future studies designed to demonstrate the benefits of HIIT in older populations.

We also hypothesize that participants who complete 12-weeks of HIIT and then become sedentary over the following 16-months will demonstrate reduced fitness, function, and quality of life, along with alterations in key underlying biological processes.

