Functional capacity using the SPPB that includes a chair rise test, balance and coordination testing, and a gait speed test. We will also conduct surveys to assess activities of daily living (ADLs) and the quality of life, enjoyment, and satisfaction questionnaire – short form (Q-LES-Q-SF) during consultation to assess general well-being and perceived quality of life. We will also conduct the physical activity enjoyment scale (PACES) survey [43] to determine the participant's perceived enjoyment of the exercise protocol. Additionally, free-living physical activity will be assessed using a Fitbit activity monitor over the course of 7 days. Sleep quality will be determined using the Pittsburgh Sleep Quality Index (PSQI).

Next-GEN miRNA-SEQ: We will isolate RNA and perform RNA-SEQ analysis to determine the quality (miRNA purification, total sequence reads, and unique miRNAs identified) and whether we can identify differentially expressed miRNAs. As depicted in the preliminary results, we will also perform principal component analyses on the complete miRNA profiles. We expect to identify miRNA species that with future studies may provide potential pathways to better understand how de-training / de-conditioning impact function and quality of life.

Metabolomics

Recovery Measures: A graded cycle exercise test will be administered to assess changes in pulse rate and skeletal muscle hemodynamic response to an acute exercise challenge. A ramped protocol will be utilized beginning with 1-minute of cycling with resistance increasing incrementally with each minute of exercise. The test will be terminated by the participant

based upon dyspnea or lower-limb fatigue. Each test will begin and end with a 10-minute rest phase for baseline measurement purposes. Serum collection will take place before and immediately after each graded exercise test.

Skeletal muscle hemodynamic response: Continuous functional near infrared spectroscopy (fNIRS) will be utilized to assess changes in regional blood flow and oxygen saturation within the exercising quadriceps muscle of each research subject. Tissue oxygen saturation is highly correlated to cardiorespiratory fitness and is used to measure physiological adaptation to exercise training. Use of this non-invasive measurement technique will allow us to better quantify how subjects respond to high intensity interval training.

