8.0 Vulnerable Populations

If the research involves special populations that are considered vulnerable, describe the safeguards included to protect their rights and welfare.

NOTE: You should refer to the appropriate checklists, referenced below, to ensure you have provided adequate detail regarding safeguards and protections. You do not, however, need to provide these checklists to the IRB.

8.1 *For research that involves **pregnant women**, safeguards include:*

NOTE CHECKLIST: Pregnant Women (HRP-412)

Response: **N/A:** This research does not involve pregnant women.

8.2 *For research that involves **neonates of uncertain viability or non-viable neonates**, safeguards include:*

NOTE CHECKLISTS: Non-Viable Neonates (HRP-413), or Neonates of Uncertain Viability (HRP-414)

Response: **N/A:** This research does not involve non-viable neonates or neonates of uncertain viability.

8.3 *For research that involves **prisoners**, safeguards include:*

NOTE CHECKLIST: Prisoners (HRP-415)

Response: **N/A:** This research does not involve prisoners.

8.4 *For research that involves **persons who have not attained the legal age for consent to treatments or procedures involved in the research (“children”)**, safeguards include:*

NOTE CHECKLIST: Children (HRP-416)

Response: **N/A:** This research does not involve persons who have not attained the legal age for consent to treatments or procedures (“children”).

8.5 *For research that involves **cognitively impaired adults**, safeguards include:*

NOTE CHECKLIST: Cognitively Impaired Adults (HRP-417)

Response: **N/A:** This research does not involve cognitively impaired adults.

8.6 *Consider if other specifically targeted populations such as students, employees of a specific firm, or educationally or economically disadvantaged persons are vulnerable. Provide information regarding their safeguards and protections, including safeguards to eliminate coercion or undue influence.*

Response: The possibility exists that economically disadvantaged individuals may be included in our study, although this group is not specifically targeted.

Participants will be receiving remuneration for their effort, however, the amount chosen (~\$400) is fair based on the length of the study and that travel to the VAMC during the 3-4-month period is required.

For the post-HIIT examination, participants will be provided with a Fitbit activity monitor and \$250 dollars for their participation.

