11.0 Procedures Involved

11.1 Provide a description of **all research procedures or activities** being performed and when they are performed once a subject is screened and determined to be eligible. Provide as much detail as possible.

NOTE: This should serve as a blueprint for your study and include enough detail so that another investigator could pick up your protocol and replicate the research. For studies that have multiple or complex visits or procedures, consider the addition of a schedule of events table in in your response.

Response: Our study involves several procedures, surveys, and questionnaires that will be administered during baseline and end point assessments. These include the following:

Frailty Assessment: Frailty is determined based upon assessment of grip strength (using a Jamar hand grip dynamometer, Average of the best 3 of 5 attempts from the dominant hand), gait speed (Time to walk 15 feet), body weight change (participant questioned if they have experienced unexpected weight loss of 10% or greater over the past year), and surveys to assess endurance and activity levels (Survey instruments attached).

Short physical performance battery (SPPB): The SPPB is an assessment of functional capacity based upon gait speed (using data from frailty), chair rise test (participant is instructed to rise from a seated position as many times as possible within 30 seconds), and balance and coordination (participant is asked to stand, stand with one foot in front of another, and stand with feet in an offset position).

Functional capacity and quality of life surveys: To assess functional capacity we will also administer an activities of daily living survey (ADLs – survey instrument attached), the quality of life, enjoyment, and satisfaction survey (Q-LES-Q-SF, instrument attached), and the physical activity enjoyment scale (PACES, instrument attached) to assess perceived enjoyment of the exercise protocol.

Mental status: To assess mental status we will administer the VA-ST. Louis university Mental Status (SLUMS) examination (instrument attached)

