Regional Tissue Oxygen Saturation: fNIRS will be used to measure blood flow to each subject's exercising quadriceps muscle during the maximal exercise test. The fNIRS device will be strapped atop the right quadriceps muscle using a neoprene sleeve prior to the VO₂max test and will remain in place through cessation of exercise and recovery. The fNIRS device communicates wirelessly via Bluetooth to a laptop computer for data acquisition. The fNIRS device is both small (~5 cm x ~7 cm x ~2.5 cm) and non-invasive.

Functional capacity and quality of life surveys: To assess functional capacity we will also administer an activities of daily living survey (ADLs - survey instrument attached), the quality of life, enjoyment, and satisfaction survey (Q-LES-Q-SF, instrument attached), and the physical activity enjoyment scale (PACES, instrument attached) to assess perceived enjoyment of the exercise protocol. In addition, the Pittsburgh Sleep Quality Index (PSQI – instrument attached) will be administered. For a duration of 7-days, leisure-time physical activity will be measured using Fitbit activity monitors.

Mental status: To assess mental status we will administer the VA-ST. Louis university Mental Status (SLUMS) examination (instrument attached) as well as the Cognivue Clarity.

Serum Collection: When participants return for the post-HIIT visit, we will also collect 80 mL as a follow-up to the previous analysis as well as to be used in blood cell metabolism experiments.

11.2 Describe what data will be collected.

NOTE: For studies with multiple data collection points or long-term follow up, consider the addition of a schedule or table in your response.

Response:

Participants' basic demographics (age, gender, race)

Past medical history as it pertains to inclusion/exclusion criteria (co-morbidity status)

Frailty status and parameter scores (Gait speed, weight change, grip strength, activity and endurance)

Short physical performance battery status and parameter scores (Gait speed, chair rise test, balance testing)

Mental status score (VA SLUMS instrument and Cognivue Carity)

Activities of daily living score (ADLs instrument)

Quality of life score (Q-LES-Q-SF instrument)

Physical activity enjoyment score (PACES instrument)

Sleep Quality (PSQI Instrument)

Leisure-time physical activity (Fitbit activity monitor)

Heart rate max score (VO2max test)

Quadriceps strength (MicroFET2 device)

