12.0 Study Timelines

12.1 Describe the anticipated duration needed to enroll all study subjects.

Response: 18 months from the start date of funding (October 1st, 2018)

The post-training assessment will be completed by September 28th, 2021.

12.2 Describe the duration of an individual subject's participation in the study. Include length of study visits, and overall study follow-up time.

Response: Once enrolled in the study the participant will be administer baseline assessment protocols that combined will take approximately 2 hours. The individual will then perform 12 sessions (3 per week – Monday, Wednesday, and Friday) of HIIT exercise. The exercise protocol plus body weight and blood pressure measurements will take no more than 20 minutes. A final assessment will also take approximately 2 hours. Participants in the post-HIIT examination will be required to participate for one additional visit.

12.3 Describe the estimated duration for the investigators to complete this study (i.e. all data is collected and all analyses have been completed).

Response: Two years from the enrollment of the last participant. Post-HIIT assessment will require three months to complete.

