23.0 Potential Benefits to Subjects

23.1 Describe the potential benefits that individual subjects may experience by taking part in the research. Include the probability, magnitude, and duration of the potential benefits. Indicate if there is no direct benefit.

NOTE: Compensation cannot be stated as a benefit.

Response: This research has the potential to improve functional capacity and quality of life in study participants. This study also introduces participants to a maintainable exercise strategy for older individuals, who previously may not have considered exercise to be a viable option to maintain functional capacity.

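### The de-training hypothesis depends on participants having become sedentary after HIIT, but the protocol text describes no activity history since HIIT and no rule for who counts as sedentary, and the 7-day Fitbit reading has no earlier value to compare with

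*Combined protocol and SAP*

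**What the plan says.** Section 1.2 predicts that "participants who complete 12-weeks of HIIT and then become sedentary over the following 16-months will demonstrate reduced fitness, function, and quality of life". Section 1.1 describes the follow-up more broadly: the team will approach people already enrolled and "ask them to return for 1 follow-up visit in order to investigate changes in physical fitness, muscle strength, physical activity, functional capacity", among other outcomes, in those who completed the training. Section 12.2 confirms a single contact: "Participants in the post-HIIT examination will be required to participate for one additional visit". Section 6.1 puts the number due a final visit at 27.

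Activity is to be assessed in two ways.

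- **Device.** Among the follow-up parameters in section 5.1, "free-living physical activity will be assessed using a Fitbit activity monitor over the course of 7 days". The follow-up procedures in 11.1 say the same: "For a duration of 7-days, leisure-time physical activity will be measured using Fitbit activity monitors". Section 8.6 ties issue of the device to that visit: "For the post-HIIT examination, participants will be provided with a Fitbit activity monitor".
- **Self-report.** The frailty assessment in 11.1 includes "surveys to assess endurance and activity levels". It appears in the baseline and endpoint procedures and again in the follow-up procedures.

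Section 18.1 plans paired t-tests of baseline against endpoint. It contains no follow-up contrast and no activity variable. The exploratory aim numbered 3.0, under Scientific Endpoints, concerns change 16 months after the programme and sets no condition on activity.

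**The concern.** The hypothesis is about people who stopped exercising. The people to be tested are all completers who return. These are the same group only if everyone stopped, and the protocol text gives no way to find out.

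Interpretation is what is at stake. If fitness and function have held up at follow-up, the gains may persist without training, or enough people may have kept training. If they have fallen, the loss would be attributed to de-training without knowing who de-trained. The miRNA work is affected in the same way, because section 5.1 proposes to read the follow-up profiles in terms of de-training and de-conditioning. Section 1.1 also promises information on change in physical activity, and the device cannot supply it.

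This is separate from the absence of a follow-up test in 18.1. If that test were added, it would still be applied to all returners and not to the group named in 1.2.

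**Working it through.** The plan states no figure on this point, so there is nothing to reproduce. The check sets each activity measure against each time point.

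| Measure | Baseline | Endpoint | Between endpoint and follow-up | Follow-up |
|---|---|---|---|---|
| Activity survey within the frailty assessment (11.1) | yes | yes | none planned | yes |
| Fitbit, 7 days (5.1, 8.6, 11.1) | no | no | none planned | yes |
| Exercise history since HIIT | – | – | – | not described |
| Rule defining sedentary | – | – | – | not given |

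Section 11.2 lists the Fitbit among all data collected without giving a time point. The procedures place it only at follow-up.

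**Share of the interval the device could represent**

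- Interval: 16 × 365.25/12 = 487 days.
- Device share: 7/487 = 0.0144, or about 1.4%.
- This is an upper limit. If the monitor is handed out at the visit and worn afterwards, it samples none of the interval.

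**Change in activity**

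- Device: there are 0 readings before follow-up, so no change can be calculated for any of the 27.
- Survey: three readings are planned, so change in self-reported activity can be calculated. The documents do not say what period the questions cover. The forms were attached to the submission and are not reproduced.

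**Effect of pooling**

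Let p be the share who kept exercising, L the mean loss in those who stopped, and rL the mean loss in those who continued. Then

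pooled mean loss = (1 − p)L + p·rL = L[1 − p(1 − r)].

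The documents give neither p nor r, so the values below are assumptions that show the range only.

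| p | r = 0 (continuers lose nothing) | r = 0.5 | r = 1 (continuers lose as much) |
|---|---|---|---|
| 0 | 0% smaller | 0% smaller | 0% smaller |
| 0.25 | 25% smaller | 12.5% smaller | 0% smaller |
| 0.50 | 50% smaller | 25% smaller | 0% smaller |

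Within this range the dilution runs from nothing to half. The plan as written would collect no exercise history from which p could be estimated.

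**The case against.** **Activity is measured, and a participant-level rating exists.** This stands in part. A reader might infer that activity goes unmeasured apart from the Fitbit. The documents do not support that: the survey is repeated at all three visits, section 11.2 lists its score as collected data, and section 4.1 names low activity as a frailty criterion. A low-activity rating at follow-up is therefore planned. It does not close the gap as written. The text does not say that it covers the 16 months, nothing links it to the word sedentary in 1.2, and 18.1 does not use it. Because the forms are not shown, the point is limited to what the protocol text describes.

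**Nothing shows that anyone kept exercising.** Correct. Section 23.1 says that the study "introduces participants to a maintainable exercise strategy for older individuals". A reader might take this as an expectation that some would continue. It is a statement of potential benefit and says nothing about what participants did. Equally, no section says that everyone stopped, and the pandemic restrictions mentioned in 1.1 do not establish it.

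**The aim is exploratory.** True, and the primary aim (recruitment and attrition) is untouched. The unconditional aim numbered 3.0 can be answered in all returners. Only section 1.2 adds the sedentary condition, so rewording that section is a legitimate remedy. The exploratory status lowers the weight of the point without removing it, since 1.2 is stated as a hypothesis.

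**Splitting the group gives no clean estimate.** This stands. The stopped group would be small and self-selected, and some may have stopped because of illness or injury. Its results should be descriptive.

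**Conclusion.** The concern holds as a cheap improvement. The hypothesis in 1.2 is conditional on becoming sedentary. No measurement is planned during the interval, the protocol text describes no activity history since HIIT, and no rule identifies who became sedentary. The Fitbit week shows current activity only. The repeated survey could show change in self-reported activity, but the plan does not assign it that role. A pooled result therefore could not distinguish lasting gains from continued training.

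No size can be put on the bias. A reader might infer a loss understated by 25% or 50%, but those figures need an assumed share of continuers and the further assumption that continuers lost nothing. The documents support neither. The ambiguity of interpretation depends on neither figure, only on there being no record of who stopped.

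**What to change.** 1. At the follow-up visit, before testing, record the type, weekly frequency and months of exercise since the last HIIT session.
2. Define stopped and continued by a rule written down before any follow-up results are seen.
3. Add to 18.1 the change from endpoint to follow-up. Report it for all returners as the main result and for the stopped group descriptively.
4. Limit de-training wording, including for miRNA, to the stopped group. Alternatively, reword 1.2 as change 16 months after HIIT regardless of activity, which matches the aim numbered 3.0.
5. Name the repeated frailty activity survey as the measure of change in physical activity, and state its recall window. Describe the Fitbit week as current activity only.

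The cost is a few interview questions at a visit already planned, plus amendment wording. Timing matters because no later contact is planned at which the history could be taken. The downsides are recall error over 16 months, a small stopped subgroup out of at most 27, and a non-randomised split that illness or injury may confound. Choosing the rewording in step 4 avoids the split, but gives up any claim about de-training as such.

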2.0 Scientific Endpoints

2.1 Describe the scientific endpoint(s), the main result or occurrence under study.

*NOTE: Scientific endpoints are outcomes defined before the study begins to determine whether the objectives of the study have been met and to draw conclusions from the data. Include primary and secondary endpoints. Some example endpoints are: reduction of symptoms, improvement in quality of life, or survival. Your response should **not** be a date.*

Response: This is a longitudinal study to assess changes in function and physiological parameters following a 3-month exercise intervention.

The Primary Aim is to assess recruitment and attrition rates as benchmarks to gauge the feasibility of administering High Intensity Interval Training in older individuals.

Our secondary aim is to assess the feasibility of assessing maximal respiration (VO₂max), quadriceps strength, frailty status, functional capacity (Short physical performance battery), quality of life status, attrition rates, serum inflammatory biomarkers, testosterone, miRNA, and change in skeletal muscle regional blood flow and oxygen saturation in response to HIIT training.

3.0 In addition, we will explore how fitness, function, and quality of life change 16-months after completion of a 12-week HIIT program among adults 60 – 90 years old.

4.0 Background

4.1 *Provide the scientific or scholarly background, rationale, and significance of the research based on the existing literature and how it will contribute to existing knowledge. Describe any gaps in current knowledge. Include relevant preliminary findings or prior research by the investigator.*

Response: Frailty is characterized by reduced physiological function that increases vulnerability to greater dependency and/or death [1], as well as a greater allocation of resources to achieve requisite care [2]. Fried et al. defined frailty as including three or more of the following: diminished gait speed, reduced grip strength, unintentional weight loss, low activity, and fatigability [1]. Pre-frail individuals exhibit 1 or 2 of the characteristics. Exercise is beneficial for frailty [3-5], yet only 12% of individuals over the age of 65 participate in exercise activities such as strength training [6]. Lack of time, length of exercise sessions, and injury concerns are cited as the most common barriers to participation [7-9]. High intensity interval training (HIIT), with short sessions and less time commitment, is emerging as an alternative to standard exercise. Even with lower time investment, HIIT has often been shown to be equivalent or better than MICT for improving fitness, including increasing VO₂max, heart function, aerobic fitness, and perceptions of health-related quality of life [10-13]. However, these studies did not examine frail or older adults.

HIIT has been safely administered to vulnerable populations in numerous reports. Fiatarone et al. [14] pioneered the use of a progressive resistance HIIT as an intervention for the very old in a study involving frail nonagenarians (age 90 ± 1) and found excellent tolerance while improving strength and gait speed over 10 weeks. Furthermore, an uphill treadmill walking HIIT regimen, featuring 4 x 4

minute intervals at 85-95% HRmax with a total time of 25 minutes, has been shown to be safe and effective in 70-year-old men [15], as was a 12 x 1 minute walking intervals with a total time of 23 minutes in 75-85 year old women [16]. HIIT has also been successfully implemented in patients with significant co-morbidities, including congestive heart failure [17], coronary artery disease [18], and chronic obstructive pulmonary disease [19]. Additionally, a systematic review including 4,846 patients with coronary heart disease across 175,820 training hours found the risk of cardiovascular events related to HIIT to be low [20]. However, the exciting aspect of HIIT is the low time commitment; in particular short session HIIT regimens (\leq 10 minutes total and only \leq 4 minutes at high intensity) have demonstrated physiological benefits that were comparable to longer MICT regimens [21-24]. To our knowledge short session HIIT has not been attempted in individuals older than 65 years of age. However, our recently published pre-clinical study [25] demonstrates that a 3-times-a-week program of 4 x 1 minute intense intervals for a total of 10 minutes markedly improved muscle mass and quality, physical performance, and reduced frailty in old mice. To our knowledge there are no studies that investigate the therapeutic potential of short-session high intensity interval training in individuals >65 years of age.

4.2 Include complete citations or references.

Response:

1. Fried, L.P., C.M. Tangen, J. Walston, et al., Frailty in older adults: evidence for a phenotype. *J Gerontol A Biol Sci Med Sci*, 2001. 56(3): p. M146-56.
2. Lutomski, J.E., M.A. Baars, H. Boter, et al., [Frailty, disability and multi-morbidity: the relationship with quality of life and healthcare costs in elderly people]. *Ned Tijdschr Geneeskd*, 2014. 158: p. A7297.
3. de Vries, N.M., C.D. van Ravensberg, J.S. Hobbelin, et al., Effects of physical exercise therapy on mobility, physical functioning, physical activity and quality of life in community-dwelling older adults with impaired mobility, physical disability and/or multi-morbidity: a meta-analysis. *Ageing Res Rev*, 2012. 11(1): p. 136-49.
4. Vina, J., A. Salvador-Pascual, F.J. Tarazona-Santabalbina, et al., Exercise training as a drug to treat age associated frailty. *Free Radic Biol Med*, 2016. 98: p. 159-64.
